## 3.3.4 Restrictions

Subjects will be required to:

- 1. Refrain from alcohol, grapefruit containing products, and apple juice from CRC admission through the final study evaluation
- 2. Refrain from using over-the-counter (OTC) medications, and herbal supplements 2 weeks prior to CRC admission through the final study assessments
- 3. Refrain from eating or drinking starting 8 hours before study drug administration and continuing through 4 hours post study drug administration (with the exception of water which will be allowed ad lib until 2 hours prior to study drug administration and 2 hours post study drug administration). Lunch will be served approximately 4 hours after the dose of rosuvastatin. At all other times during the in-patient period, subjects will be served standard meals on a regular basis.

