# 1.5 Safety

Review of adverse event data show that rosuvastatin is well tolerated. The overall frequency of alanine aminotransferase (ALT) elevations is low. Clinically significant ALT elevations (>3 x the upper limit of normal (ULN) on 2 or more occasions) are uncommon and for the most part resolve with either continued therapy with or without dose reduction or after an interruption of treatment. No cases of irreversible liver injury secondary to rosuvastatin therapy have been identified.

Muscle-related findings (ie, creatine kinase (CK) increases, myalgia, and myopathy) are a well-recognized complication of statin therapy. The frequency of both myalgia and CK elevations is low and similar in the 10 mg to 40 mg dose range. Only 1 case, (at 20 mg dose), of myopathy – defined as CK elevations >10 x ULN associated with muscle symptoms – was considered possibly related to rosuvastatin therapy in the 10 mg to 40 mg dose range. The frequency of these complications in subjects given rosuvastatin is consistent with the data reported for other marketed statins.

The analysis of renal data indicates that proteinuria, predominantly tubular in nature, occurs at a low frequency among subjects receiving rosuvastatin in doses up to and including 40 mg. A low frequency of proteinuria was also observed in subjects treated with other statins in the rosuvastatin clinical program. The proteinuria seen with rosuvastatin is not associated with clinically significant increases in serum creatinine or worsening renal function. The 40 mg rosuvastatin dose is well tolerated in terms of renal effect with both shorter-term and longer-term treatment.

Rosuvastatin is well tolerated in a broad spectrum of subjects independent of gender, age, race, menopausal status, or the presence of comorbid conditions such as hypertension, diabetes, coronary heart disease, or altered hepatic or renal function.

Rosuvastatin can be administered with a range of medications used to treat either comorbid medical conditions or underlying lipid profile abnormalities.

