# 3. STUDY PLAN AND PROCEDURES

# **3.1** Overall study design

This is a single-center, open label, single dose, pharmacokinetic study of subjects having Chinese, Filipino, Asian-Indian, Korean, Vietnamese, and Japanese heritage and are residing in the United States. Approximately156 subjects will be recruited with a minimum of 22 subjects and a maximum of 26 subjects from each ethnic group to obtain at least 132 evaluable subjects. Approximately 26 healthy Caucasian subjects will be recruited to obtain at least 22 evaluable subjects. These subjects will serve as a control group for the study.

Rosuvastatin exposure following a single oral dose of 20 mg will be determined by measuring  $C_{max}$  and AUC. In addition,  $AUC_{(0-t)}$ ,  $t_{1/2\lambda Z}$ ,  $t_{max}$ , and CL/F of rousuvastatin and  $C_{max}$ , AUC,  $AUC_{(0-t)}$ ,  $t_{1/2\lambda Z}$ , and  $t_{max}$ , of N-desmethyl rosuvastatin and rosuvastatin lactone will be measured.

Subjects satisfying the inclusion and exclusion criteria and screening exams will enter the clinical research center (CRC) on Day -1. On Day 1 subjects will receive a single dose of rosuvastatin 20 mg under fasting conditions. Blood samples will be taken pre-dose (within 30 minutes) and 0.5, 1, 2, 3, 4, 5, 6, 8, 10, 12, 18, 24, 30, 36, 48, 54, 60, and 72 hours post-dose. After completion of the final blood sample and all safety assessments on Day 4, the subjects will be discharged.

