#### **3.4.2 Doses and treatment regimens**

On the morning of Day 1, all subjects will receive a single 20 mg dose of rosuvastatin calcium under fasting conditions (See restrictions Section 3.3.4). Tablets will be taken orally with 240 milliliters (mL) of distilled, room temperature water. Tablets are not to be crushed or chewed. Subjects must remain in an upright position (sitting or standing) for 4 hours after dosing.

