# 6.4.4 Laboratory data

All laboratory safety data, incorporating hematology, clinical chemistry, lipid profiles, and urinalysis data will be listed, with deviations from the normal range explicitly noted on the listings.

Continuous laboratory data will be summarized using standard summary statistics. Both absolute values and change from pre-dose baseline will be summarized.

Discrete laboratory data will be summarized using standard summary statistics.

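### Alcohol abstinence starts only at admission and exercise is unrestricted, so the pre-dose CK and ALT baseline is free-living while the only post-dose value follows confinement (minor; cheap to improve)

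*Protocol*

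**What the plan says.** - **Alcohol and juices.** Section 3.3.4 item 1 reads "Refrain from alcohol, grapefruit containing products, and apple juice from CRC admission through the final study evaluation". Section 3.1 says that subjects "will enter the clinical research center (CRC) on Day -1", so no abstinence is required before Day -1. During the stay the site provides the food: "At all other times during the in-patient period, subjects will be served standard meals on a regular basis".
- **Other products.** Item 2 of the same list does have a lead-in: "Refrain from using over-the-counter (OTC) medications, and herbal supplements 2 weeks prior to CRC admission through the final study assessments". Section 3.4.5 repeats the two weeks.
- **Exercise.** No section restricts it, before or during the stay. The only activity rule is the four hours upright after dosing in section 3.4.2.
- **Other control of alcohol.** Exclusion 8 in section 3.3.3 covers a history of abuse in the past year. The urine drug screen in section 4.1.3 does not list alcohol.
- **Laboratory draws.** The study plan (section 3, Table 1) has clinical chemistry at screening, Day -1 and Day 4, and Table 5 counts three samples. CK and ALT are in the panel (section 4.4.5). Section 4.4.1 requires a 10-hour fast before these samples.
- **Analysis.** Section 6.4.4 states "Both absolute values and change from pre-dose baseline will be summarized". It does not say whether screening or Day -1 is the baseline.
- **Why CK is of interest.** Section 1.5 names muscle findings, including CK increases, as a known complication of the statin class, and says of rosuvastatin that "The frequency of both myalgia and CK elevations is low and similar in the 10 mg to 40 mg dose range".

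**The concern.** Safety and tolerability form a secondary objective (section 2.2), assessed partly by laboratory tests. A change from baseline isolates the drug only if the two measurements are taken under similar conditions apart from the drug. Here they are not. The pre-dose draw comes from a person who may have exercised hard or drunk alcohol in the preceding days. The post-dose draw comes from the same person after several days in a research unit without alcohol.

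If exertion raises CK and alcohol raises ALT, the baseline is too high for some subjects and the change is pulled downwards. For a safety summary that is the unfavourable direction, because it works against seeing a rise. Subject restrictions are fixed in the protocol, and no later analysis can recover what a subject did before an uncontrolled baseline.

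**Working it through.** The plan gives no figure to reproduce, so the check sets the conditions of the draws side by side and then illustrates what could follow.

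**Step 1. Conditions at each draw**

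| Draw | Alcohol rule in force beforehand | Exercise rule | Fast |
|---|---|---|---|
| Screening (within 35 days of Day -1) | none | none | 10 h |
| Day -1 | from admission the same day | none | 10 h |
| Day 4 | since admission on Day -1 | none written; subject is an in-patient | 10 h |

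The fast is common to all three draws. It excludes drinking in the last hours before each sample, but says nothing about the days before that or about exertion.

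**Step 2. Length of the controlled period**

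The protocol gives no clock times. Assume dosing at 08:00 on Day 1 and admission between 08:00 and 22:00 on Day -1.
- Admission to dose: 10 to 24 hours.
- Admission to the 72-hour sample on the morning of Day 4: 72 + 10 = 82 hours to 72 + 24 = 96 hours.

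The Day 4 draw, taken around that last sample, therefore follows roughly 82 to 96 hours of in-patient conditions. The Day -1 draw follows at most a few hours of them, and the screening draw none.

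**Step 3. Can the shift be separated from the drug?**

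The study is open-label with a single treatment. The Caucasian control group also receives 20 mg (section 3.4.2), so it is a control for ethnicity and not for treatment. No untreated group goes through the same confinement. Section 4.1.6 keeps meal contents, including liquids, off the CRF, so alcohol intake before admission cannot be reconstructed from the database.

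**Step 4. Illustration, all inputs assumed**

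Set the resting value to 1. Let a share p of subjects have a baseline raised k-fold that has returned to rest by Day 4, and let the drug multiply the resting value by r.
- One subject with k = 2 and r = 1.5: observed Day 4/baseline ratio = 1.5/2 = 0.75. A true rise appears as a fall.
- Mean baseline = 1 + p(k - 1). With p = 0.10 and k = 1.5 it is 1.05 (5% inflation). With p = 0.30 and k = 3 it is 1.60 (60% inflation).
- Mean change when r = 1.5: true value +0.50; observed 1.50 - 1.05 = +0.45 down to 1.50 - 1.60 = -0.10.
- Mean change when the drug does nothing (r = 1): 1 - 1.05 = -0.05 down to 1 - 1.60 = -0.60.

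These figures show direction and how far the mean could move. They are not estimates, because the protocol gives no value for p, k or r. That exertion raises CK and alcohol raises ALT is likewise a general assumption and is not stated in the protocol.

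**The case against.** **The change score is not the only readout.** Section 6.4.4 also reports absolute values and lists all laboratory data with out-of-range results marked. A clearly abnormal Day 4 CK or ALT is therefore visible whatever the baseline was. Section 6.4 includes the median, and in the illustration 70% to 90% of subjects have a clean baseline, so the median change stays at +0.50. The objective is secondary and descriptive. All of this stands, and it is why the point is minor.

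**The baseline is not defined as Day -1.** This is true, and the definition may properly sit in the SAP. It does not remove the problem, because the screening draw is no better controlled.

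**The two-week rule for OTC and herbal products is no benchmark for alcohol or juice.** Agreed. It shows only that this list already uses a lead-in elsewhere.

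**Nothing here is a contradiction.** Also agreed. This is a design choice that could be improved at little cost.

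A reader might infer three stronger points, none of which the document supports:
- *The dose, and with it Cmax and AUC, is unprotected.* The restriction is in force from Day -1 through dosing, and item 3 adds "Refrain from eating or drinking starting 8 hours before study drug administration", apart from water. Section 1.2 describes limited metabolism, with the main metabolite formed principally by CYP2C9, and reports no juice interaction or duration. Nothing shows that juice taken before admission changes exposure the next morning, or that intake differs between ethnic groups.
- *Subjects may drink right up to the Day -1 sample.* The 10-hour fast in section 4.4.1 rules this out.
- *Healthy volunteers will be wrongly excluded.* Exclusion 4 rests on a review of history, examination and laboratory results together, and sets no CK or ALT cut-off.

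**Conclusion.** The point holds as a minor one. Section 3.3.4 controls alcohol only from admission and nothing in the protocol controls exercise, so every available pre-dose CK and ALT value is free-living apart from a 10-hour fast, while the single post-dose value follows about 82 to 96 hours in the unit (on the assumed clock times). Without an untreated arm, a fall from rest and abstinence cannot be separated from a drug effect and can hide a rise in the change-from-baseline summary.

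The size cannot be derived from the protocol; the 5% to 60% inflation of the mean baseline rests wholly on assumed inputs. The conclusion also assumes that in-patient subjects are less active than at home, which the protocol does not state. The consequence is confined to one secondary descriptive safety summary, and absolute values and out-of-range flags remain as a safeguard. No effect on the primary pharmacokinetic endpoints is shown.

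**What to change.** Amend section 3.3.4 so that alcohol abstinence and avoidance of strenuous exercise both begin a short period before the Day -1 chemistry and continue to the Day 4 draw. The sponsor should choose and justify the length. About 72 hours would be one example, and that figure is an assumption not taken from the protocol. Record compliance at the inclusion/exclusion check already planned for Day -1. The change helps only if the Day -1 draw is the baseline for CK and ALT change, so the analysis should use that draw.

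Schedule the period so that it does not overlap the three diet-diary days in section 4.1.6, when subjects are asked to keep to their usual eating habits and record all they consume. The 35-day screening window leaves room: three diary days plus an assumed three days of abstinence is six days.

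The cost is two lines in the restriction list and the subject instructions, a slightly longer lifestyle restriction, a scheduling constraint around the diary, and an occasional rescheduled admission. No extra sample or visit is needed.

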#### **3.3.5** Discontinuation of subjects from treatment or assessment

Subjects may be discontinued from study treatment and assessments at any time, at the discretion of the investigator(s).

#### 3.3.5.1 Criteria for discontinuation

Specific reasons for discontinuing a subject from this study are:

- 1. Voluntary discontinuation by the subject, who is at any time free to discontinue their participation in the study without prejudice to further treatment
- 2. Safety reasons as judged by the investigator or AstraZeneca
- 3. Eligibility criteria not fulfilled
- 4. At investigator's discretion

#### 3.3.5.2 Procedures for discontinuation

Subjects who discontinue from the study should always be asked about the reason(s) for their discontinuation and about the presence of any adverse events. If possible, they should be seen and assessed by an investigator(s). Adverse events should be followed up and the subject should return any diary cards, questionnaires and investigational products.

Discontinuation of any subject should be communicated to AstraZeneca. All withdrawals due to a serious adverse event (SAE) must be reported to AstraZeneca within 1 day. Withdrawals due to the occurrence of a non-serious AE must be reported to AstraZeneca within 15 days.

Where possible, subjects must be followed up for 30 days after completion of the study.

There must be at least 22 evaluable subjects per ethnic group; therefore, if a subject is discontinued before completing the study he/she may be replaced as needed at the discretion of the sponsor.

## **3.4** Treatment(s)

#### **3.4.1** Investigational product(s)

Rosuvastatin calcium 20 mg will be supplied as tablets for oral use.

#### **3.4.1.1** Identity of investigational product

#### Table 2Identity of investigational product

Investigational product	Dosage form and strength	Manufacturer	Formulation number
Rosuvastatin calcium	20 mg	AstraZeneca Pharmaceuticals, LP	F12673

## 3.4.1.2 Labeling

Rosuvastatin calcium 20 mg will be provided in bottles containing 100 tablets per bottle. Each subject will be assigned a bottle of rosuvastatin. Each bottle will be affixed with a twopanel label with tear-off. At least the study number, storage conditions, dosing instructions, and bottle contents will appear on both portions of the label.

Before dispensing the first dose, the date dispensed and the subject's initials and subject number must be written on both the permanent and tear off labels. The tear off portion will be removed from the bottle assigned to the subject and affixed to the appropriate CRF.

## 3.4.1.3 Storage

Study medication supplies must be stored in a secure place (eg locked cabinet) and will be accessible only to the persons authorized to dispense them to the subjects. Rosuvastatin tablets will be stored at 20-25°C (68-77  $^{\circ}$ F) and protected from light and moisture.

#### 3.4.1.4 Accountability

The investigational product provided for this study is for use only as directed in the protocol. The AstraZeneca site monitor will return all unused investigational product to

. The investigational

site personnel will account for all drugs dispensed and returned. Certificates of delivery and return must be signed.

#### **3.4.2 Doses and treatment regimens**

On the morning of Day 1, all subjects will receive a single 20 mg dose of rosuvastatin calcium under fasting conditions (See restrictions Section 3.3.4). Tablets will be taken orally with 240 milliliters (mL) of distilled, room temperature water. Tablets are not to be crushed or chewed. Subjects must remain in an upright position (sitting or standing) for 4 hours after dosing.

## **3.4.3** Method of assigning subjects to treatment groups

Written informed consent will be obtained before enrollment. Each subject will be assigned a unique enrollment number that will identify the site and the ethnic group of the subject enrolled. (See Table 3) This table is representative and the number of sites participating may be more or less than those listed.

Subjects fulfilling the eligibility criteria and continuing in the study will be assigned unique subject numbers that will identify the site and ethnic group of the subject. (See Table 4)

Subjects will be assigned enrollment/subject numbers consecutively as they enroll/enter into the study. If a subject discontinues from the study, the subject number will not be re-used and the subject will not be allowed to re-enter the study.

Table	Table 5 Assignment of enforment numbers						
Site #	Chinese	Filipino	Asian- Indian	Korean	Vietnamese	Japanese	Caucasian
1	E0001101*	E0001201	E0001301	E0001401	E0001501	E0001601	E0001701
2	E0002101	E0002201	E0002301	E0002401	E0002501	E0002601	E0002701

Table 3Assignment of enrollment numbers

\*This table represents the first enrollment number for each site/ethnic group. Numbers will be assigned consecutively as prospective subjects are enrolled.

Site #	Chinese	Filipino	Asian- Indian	Korean	Vietnamese	Japanese	Caucasian
1	1101	1201	1301	1401	1501	1601	1701
2	2101	2201	2301	2401	2501	2601	2701

\*This table represents the first subject number for each site/ethnic group. Subject numbers will be assigned consecutively to subjects as they are entered into the study. NB: assigned enrollment numbers will not necessarily match assigned subject numbers.

#### **3.4.4** Blinding and procedures for unblinding the study

Not applicable

#### 3.4.5 Concomitant medication

During the screening period, subjects will be instructed to consult with the investigative staff prior to taking OTC and prescription medications, dietary supplements, and herbal remedies. All medications, (OTC products, dietary supplements, and herbal remedies) will be discontinued two weeks prior to entry into the CRC. Women with a history of previous oral contraceptive use must have discontinued the regimen at least 3 months prior to Day -1.

Subjects will not be permitted to take any medication, dietary supplements, or herbal remedies during the in-patient period. Acetaminophen preparations will be allowed for analgesia, if absolutely necessary, for the well being of the subject. If acetaminophen is necessary, administration is not to exceed 2 grams in any 12-hour period.

Any medication, which is considered necessary for the subject's safety and well being, may be given at the discretion of the investigator(s). The administration of all medication (including investigational products) must be recorded in the appropriate sections of the CRF.

#### **3.4.6** Treatment compliance

Compliance will be assured by the supervised administration of the study drug by site personnel.

# 4. MEASUREMENT OF STUDY VARIABLES

## 4.1 Screening and demographic measurements

Screening of subjects will be done within 35 days of Day –1.

#### 4.1.1 Demographics

At the screening visit, demographic data will be collected including the following: date of birth, sex, and race.

Subjects being entered into the study as part of the Asian study group will self-report race by checking a tick box offered during the screening process. The following tick boxes will be offered: Caucasian, Black, Oriental, American Indian, and Other. Additional tick boxes will be provided to indicate which Asian sub-group the subject belongs. These tick boxes will include Chinese, Filipino, Asian-Indian, Korean, Vietnamese, Japanese, and Other. Subjects reporting mixed ethnicity by selecting more than one Asian sub-group or boxes indicating "Caucasian", "Black", "American Indian" or "Other" will not be included in the study.

In addition, subjects being entered into the study as part of the Asian study group will be asked to identify the race of each parent. Only those subjects with both parents matching the self-reported race (of the subject) will be eligible for the study.

Subjects being entered into the study as part of the Caucasian control group will also selfreport race by checking a tick box offered during the screening process. The same tick boxes will be offered to the control group as offered to the Asian groups. Only those choosing "Caucasian" will be considered eligible for the study. Please refer to the "Instructions for the Investigator" located in the CRF for additional direction.

## 4.1.2 Medical history/Drug history

A complete medical and drug history will be recorded for each subject at the initial screening visit and reviewed for any additions or omissions on admission to the CRC (Day -1). Significant medical conditions that have occurred within the past 2 years, or conditions that are ongoing (ie, headache, backache, indigestion) are to be recorded in the CRF. The drug history must identify any known drug allergies, presence or history of drug abuse, and use of chronic medications.

#### 4.1.3 Urine Drug Screen

A urine screen for drugs of abuse will be conducted at the times specified in Table 1.

If a test result is positive for drugs of abuse, the subject will not participate in the study. The following drugs of abuse will be screened: cannabinoids, cocaine, opiates, amphetamines, benzodiazepines, barbiturates, methaqualone, propoxyphene, and methadone.

#### 4.1.4 Complete physical examination

Each subject will undergo a complete physical examination, which will be conducted at the times specified in Table 1.

This complete physical examination will include an assessment of the following:

- General appearance,
- Skin, head, neck, and lymph nodes
- Musculoskeletal/extremities (including spine)
- Cardiovascular
- Lungs
- Abdomen
- Neurological (reflexes)

Physical examination data to be recorded on the CRF will include: 1) normal/abnormal and 2) a description of any abnormalities.

Height in centimeters (cm) and weight in kg will be measured at screening only and will be recorded on the CRF.

